## **9. SAFETY AND TOLERABILITY**

[Appendix A](#) provides a list of data displays. Sample data displays are included in a separate document.

### **9.1. General Considerations**

Summary tables may be replaced with listings when appropriate. For instance, an AE frequency table may be replaced with a listing if it only contains a few unique preferred terms reported on relatively few subjects.

### **9.2. Adverse Events**

#### **9.2.1. Adverse Event Definitions**

A TEAE is any AE either reported for the first time or worsening of a pre-existing event after the first dose of study treatment (until 30 days after the last dose of study treatment). Analysis of AEs (as discussed below) will be limited to TEAEs, but data listings will include all AEs regardless of their timing in relation to study treatment administration.

Adverse events will be tabulated by MedDRA PT and SOC. Severity of AEs will be graded using the NCI CTCAE version 4.03. The CTCAE reporting guidelines and grading details are available on the Cancer Therapy Evaluation Program website.

The subset of AEs considered by the investigator to be related to study treatment will be considered to be treatment-related AEs. If the investigator does not specify the relationship of the AE to study treatment, the AE will be considered to be treatment-related. The incidence of AEs and treatment-related AEs will be tabulated. In addition, SAEs will also be tabulated.

Any missing onset date, causality, or severity must be queried for resolution. Unresolved missing causality and severity will be handled according to the following rules:

- An unresolved missing causality will be considered treatment-related.
- An unresolved missing severity will be identified as an unknown severity.

For purposes of analysis, all AEs will be considered TEAEs unless the AE can unequivocally be defined as not treatment-emergent.

### **9.2.2. Dose-Limiting Toxicities**

The DLTs will be listed by treatment groups defined in Section 5.2 and dose levels for subjects in Parts 1 and 3.

### **9.2.3. Immune-Related Adverse Events**

For subjects receiving INCB059872 in combination with nivolumab (TGs E and E1), the number of subjects who experienced any irAEs will be summarized by SOC, PT, and maximum severity. Refer to Appendix H in the Protocol for details of irAEs.

### **9.2.4. Adverse Event Summaries**

An overall summary of AEs will include:

- Number (%) of subjects reporting any TEAEs
- Number (%) of subjects reporting any SAEs
- Number (%) of subjects reporting any Grade 3 or 4 TEAEs
- Number (%) of subjects reporting any TEAEs related to INCB059872
- [REDACTED]
- Number (%) of subjects who temporarily interrupted INCB059872 because of TEAEs
- [REDACTED]
- Number (%) of subjects who permanently discontinued INCB059872 because of TEAEs
- [REDACTED]
- Number (%) of subjects with INCB059872 dose reductions because of TEAEs
- [REDACTED]
- Number (%) of subjects who had a fatal TEAE

The following summaries will be produced by MedDRA term (if 10 or fewer subjects appear in a table, a listing may be appropriate):

- Summary of TEAEs by SOC and PT
- Summary of TEAEs by PT in decreasing order of frequency
- Summary of TEAEs by SOC, PT, and maximum severity
- Summary of Grade 3 or 4 TEAEs by SOC and PT
- Summary of Grade 3 or 4 TEAEs by PT in decreasing order of frequency
- Summary of INCB059872 treatment-related AEs by SOC and PT

- Summary of INCB059872 treatment-related AEs by PT in decreasing order of frequency
- Summary of INCB059872 treatment-related AEs by SOC, PT, and maximum severity
- Summary of Grade 3 or 4 INCB059872 treatment-related AEs by SOC and PT
- [REDACTED]
- [REDACTED]
- [REDACTED]
- [REDACTED]
- Summary of TEAEs leading to death by SOC and PT
- Summary of serious TEAEs by SOC and PT
- Summary of serious TEAEs by PT in decreasing order of frequency
- Summary of INCB059872 treatment-related SAEs by SOC and PT
- [REDACTED]
- Summary of TEAEs leading to INCB059872 dose reduction by SOC and PT
- [REDACTED]
- Summary of TEAEs leading to INCB059872 dose interruption by SOC and PT
- [REDACTED]
- Summary of TEAEs leading to discontinuation of INCB059872 by SOC and PT
- [REDACTED]

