**Table 1: Number of Subjects Who Enrolled in Study INCB 59872-101 (as of 10 JUL 2017)**

Treatment	Number of Subjects
Total number of subjects exposed to INCB059872	39
TG A: AML	17
2 mg QOD	3
2 mg QD	6
3 mg QD	5
4 mg QD	3
TG B: SCLC (and other solid tumors with medical monitor approval)	22
2 mg QOD	3
3 mg QOD	6
3 mg QD	3
4 mg QOD	7
2 mg QD	1
1 mg QD	2

Preliminary unaudited data, as of 10 JUL 2017, are presented here for 39 subjects who have been treated with INCB059872 doses of 1 mg QD, 2 mg (QOD or QD), 3 mg (QOD or QD), and 4 mg (QOD or QD). Eight subjects were receiving treatment as of the data cutoff date. Of the 39 subjects, 12 subjects have received INCB059872 for > 20 days, 14 subjects have received INCB059872 for > 30 days, and 6 subjects have received INCB059872 for > 90 days.

[Table 2](#) and [Table 3](#) summarize TEAEs in descending order that occur in at least 3 subjects total for each treatment group. The most frequent TEAEs among all dose cohorts in TG A were fatigue and nausea (6 subjects each). The most frequent TEAEs among all dose cohorts in TG B were thrombocytopenia and dysgeusia (9 subjects each).

Based on preclinical data generated to date, there is reason to believe that subjects may develop some level of thrombocytopenia. As of the data cutoff date, 6 DLTs of  $\geq$  Grade 3 thrombocytopenia or platelet count decrease have been reported in the 2 mg QD, 3 mg QD, and

4 mg QOD cohorts in TG B (1, 2, and 3 respectively). Treatment interruption occurred in the subjects with DLTs and resumed following recovery; 4 of these subjects resumed study treatment at a reduced dose (3 mg QOD).

Four treatment-emergent serious adverse events (SAEs) resulted in discontinuation of study treatment: thrombocytopenia, bile duct obstruction, epistaxis, and hypotension. With the exception of thrombocytopenia, none of these TEAEs leading to INCB59872 discontinuation were considered related to study treatment. Five treatment-emergent SAEs have resulted in death, none of which were considered related to study treatment by the investigators: leukocytosis, sepsis, pulmonary alveolar hemorrhage, respiratory failure, and gastrointestinal hemorrhage.

**Table 2: Treatment Group A: Summary of Treatment-Emergent Adverse Events Occurring in at Least 3 Subjects in Decreasing Order of Frequency by Subject Total, Any Grade (Preliminary Data From Study INCB 59872-101)**

MedDRA Preferred Term	2 mg QD	2 mg QOD	3 mg QD	4 mg QD	Total

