Number of subjects enrolled as of the data cutoff date	6	3	5	3	17
Number of subjects who had at least 1 TEAE	6	3	5	3	17
Fatigue	0	3	2	1	6
Nausea	1	2	2	1	6
Decreased appetite	2	1	1	1	5
Febrile neutropenia	1	1	1	2	5
Anaemia	0	0	2	2	4
Dysgeusia	1	0	2	1	4
Hypophosphatemia	1	0	1	2	4
Vomiting	2	1	0	1	4
Cough	1	1	1	0	3
Diarrhoea	0	1	2	0	3
Hypotension	1	1	1	0	3
Platelet count decreased	0	0	1	2	3
Weight decreased	2	0	1	0	3

**Table 3: Treatment Group B: Summary of Treatment-Emergent Adverse Events Occurring in at Least 3 Subjects in Decreasing Order of Frequency by Subject Total, Any Grade (Preliminary Data From Study INCB 59872-101)**

MedDRA Preferred Term	1 mg QD a	2 mg QD	2 mg QOD	3 mg QD b	3 mg QOD	4 mg QOD	Total
Number of subjects enrolled as of the data cutoff date	2	1	3	3	6	7	21
Number of subjects who had at least 1 TEAE	1	1	3	3	6	7	20
Thrombocytopenia	0	1	0	2	2	4	9
Dysgeusia	0	0	3	2	1	3	9
Fatigue	0	0	2	2	1	3	8
Nausea	0	0	2	0	4	1	7
Constipation	0	0	0	1	3	1	5
Platelet count decreased	0	0	1	1	1	2	5
Diarrhoea	1	0	3	0	0	1	5
Decreased appetite	0	0	1	1	2	0	4
Neutropenia	0	0	0	2	0	2	4
Abdominal pain	0	0	1	0	2	0	3
Stomatitis	0	0	0	0	2	1	3
Vomiting	0	0	1	0	2	0	3
AST increased	0	0	0	1	1	1	3

a AE data not complete for this cohort.b All subjects had a dose interruption and dose reduction to 3mg QOD in the first cycle.

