When the severity of an AE changes over time for a reporting period (eg, between visits), each change in severity will be reported as a separate AE until the event resolves. For example, 2 separate AEs will be reported if a subject has Grade 1 diarrhea, meeting the definition of an AE, that lasts for 3 days before worsening to a Grade 3 severity. The Grade 1 event will be reported as an AE with a start date equal to the day the event met the Grade 1 AE definition and a stop date equal to the day that the event increased in severity from Grade 1 to Grade 3. The Grade 3 event will also be reported as an AE, with the start date equal to the day the event changed in intensity from Grade 1 to Grade 3 and a stop date equal to the day that the event either changed severity again or resolved.

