#### **9.4.3.5. Adverse Events of Special Interest**

Based on preclinical data generated to date, there is reason to believe that subjects will develop some level of thrombocytopenia. No human data have been generated yet to support this. Additionally, there is a chance for a "rebound" effect on platelets (potentially thrombocytosis) once the drug is discontinued, but human data have not been generated to support this effect. Subjects will be monitored closely and based on CTCAE grading of thrombosis will be reported as AEs as appropriate.

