## 2.3. Study Endpoints

### 2.3.1. Primary Endpoints

- **Parts 1 and 2:** Safety and tolerability as assessed by monitoring frequency, duration, and severity of AEs, through physical examinations, by evaluating changes in vital signs and ECGs, and through clinical laboratory blood and urine sample evaluations.
- **Parts 3 and 4:** Safety and tolerability as assessed by monitoring frequency, duration, and severity of AEs, through physical examinations, by evaluating changes in vital signs and ECGs, and through clinical laboratory blood and urine sample evaluations in combinations therapies.

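### The AE tables split the main expected toxicity between two platelet preferred terms, and no planned table summarizes AE duration, a named part of the primary endpoint

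*SAP*

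**What the plan says.** SAP 2.3.1 defines the primary endpoint for all four parts as "Safety and tolerability as assessed by monitoring frequency, duration, and severity of AEs", together with examinations, vital signs, ECGs and laboratory tests.

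SAP 9.2.1 sets the unit of tabulation: "Adverse events will be tabulated by MedDRA PT and SOC". SAP 9.2.4 then lists the by-term summaries, including the "Summary of TEAEs by PT in decreasing order of frequency". Others cover maximum severity, relatedness, seriousness and action taken on INCB059872.

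Protocol 9.4.3.5, under the heading for adverse events of special interest, states that "there is reason to believe that subjects will develop some level of thrombocytopenia". Protocol Table 3 has one row for *thrombocytopenia* and another for "Platelet count decreased". When Protocol 1.6.2 counts DLTs in the text following Table 1, it treats the two terms as one toxicity.

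On recording, Protocol 8.1.2 collects AE start and end dates and says that "each change in severity will be reported as a separate AE until the event resolves".

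**The concern.** A reader who wants the rate of low platelets as an adverse event will go to the frequency table and read the top platelet row. If some subjects are coded only to the other term, that row is too low, and adding the two rows is too high when a subject has both. The related, serious and dose-action tables have the same problem. None of them yields the number of subjects with a platelet AE.

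Duration is a separate gap. The primary endpoint has three AE components: frequency, duration and severity. The tables deliver the first and third. Nothing delivers the second, so the clinical study report could not say how long the main toxicity lasts except by reading listings.

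**Working it through.** **Could the missing tables be redacted?** SAP Appendix A prints AE tables 3.2.1 to 3.2.26 with no gap in numbering. The legible and redacted by-term bullets in SAP 9.2.4, taken in order, match that list. The eight redacted ones fall where Appendix A has the ATRA/azacitidine/nivolumab tables: 3.2.11 to 3.2.14, 3.2.19, 3.2.21, 3.2.23 and 3.2.25. Table 3.2.26 covers immune-related events, again by class and term. No title refers to a grouped platelet term, an event of special interest, or duration.

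**Size of the split in TG B.** The inputs are the subject counts by cohort in Protocol Table 3. For a cohort of n subjects with a subjects on one term and b on the other, the number with either term lies between max(a, b), which is full overlap, and min(a + b, n), which is no overlap.

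| Cohort | n | Thrombocytopenia (a) | Platelet count decreased (b) | Either: minimum | Either: maximum |
|---|---|---|---|---|---|
| 1 mg QD | 2 | 0 | 0 | 0 | 0 |
| 2 mg QD | 1 | 1 | 0 | 1 | 1 |
| 2 mg QOD | 3 | 0 | 1 | 1 | 1 |
| 3 mg QD | 3 | 2 | 1 | 2 | 3 |
| 3 mg QOD | 6 | 2 | 1 | 2 | 3 |
| 4 mg QOD | 7 | 4 | 2 | 4 | 6 |
| Sum | 22 | 9 | 5 | 10 | 14 |

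The row totals of 9 and 5 reproduce the printed figures. The denominator does not: the header prints 21, but the cohorts sum to 22, which is also the number in the text of Protocol 1.6.2 and in Table 1.

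- Leading row: 9/22 = 40.9%.
- Either term: 10/22 = 45.5% to 14/22 = 63.6%.
- Shortfall: 1 to 5 subjects, or 4.5 to 22.7 percentage points.
- On the printed 21: 9/21 = 42.9% against 10/21 = 47.6% to 14/21 = 66.7%.

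By cohort, the shortfall is certain only at 2 mg QOD, where 0/3 becomes 1/3. It is possible at 3 mg QD (2/3 becomes 2 or 3 of 3), 3 mg QOD (2/6 becomes 2 or 3 of 6) and 4 mg QOD (4/7 becomes 4 to 6 of 7). There is none at 1 mg QD or 2 mg QD.

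**TG A.** Protocol Table 2 shows *platelet count decreased* in 3 of 17 subjects. *Thrombocytopenia* is not listed, so it occurred in at most 2 under the table's cut of 3 subjects. Either term therefore covers 3 to 5 of 17 (17.6% to 29.4%), and the documents show no split there.

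**Duration.** Frequency and severity each have tables (for example 3.2.2 and 3.2.4). Duration has none. Nor can it be read off single records. In the example in Protocol 8.1.2, Grade 1 diarrhea lasts 3 days and then becomes Grade 3. That gives two records, the first 3 days long, and neither is the length of the episode.

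**The case against.** The strongest reply is that platelet falls are also analysed from laboratory values, independently of AE coding. SAP 9.3.2 and Table 3.3.2 give shifts to worst post-baseline CTCAE grade, Figure 4.6.2 plots mean platelets, and Protocol 9.4.3.2 counts each subject once at worst grade. This stands. A reader might infer that the toxicity is understated across all planned outputs, and the documents do not support that; only the AE tables are affected. But the laboratory tables cannot show relatedness, seriousness, dose action or episode length. The shift percentages also use baseline-grade categories as denominators.

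A reader might also infer that the split distorts the recommended dose. It does not. Escalation and the MTD rest on DLTs defined by grade, bleeding and transfusion (Protocol 5.4.3, Table 4) and adjudicated in cohort review (5.4.6). DLTs in Parts 1 and 3 are listed individually (SAP 9.2.2), and the Part 2 stopping rule counts DLTs. Protocol 1.6.2 reports the monotherapy doses as already chosen.

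Three smaller points are fair:

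- Protocol 8.2 asks for a diagnosis where possible, which should limit splitting. The protocol's own data show both terms in use all the same.
- Protocol 9.4.3.5 promises monitoring and reporting, not a special-interest table, so its absence breaches nothing.
- The study is exploratory, and Protocol 9.4.3.1 commits only to tabulating incidence. That does not remove duration from the stated primary endpoint.

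**Conclusion.** The point holds for the AE tables and for duration. For TG B as a whole the leading platelet row is low by at least 1 and at most 5 of 22 subjects. The exact number needs subject-level overlap, which the documents do not give. It would be wrong to read this as an understatement in every cohort: one cohort is certain, three are possible and two show none. Nor do Tables 2 and 3 show a second term for neutropenia or anemia, so there is no evidence of a split there.

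The duration gap does not depend on any of these counts. A named component of the primary endpoint has no planned summary, although its data are collected.

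The figures assume that Table 3 cells count subjects and that the denominator is 22. The data are preliminary and unaudited as of 10 JUL 2017, and AE data for 1 mg QD are marked incomplete. Protocol 1.6.2 gives 1 DLT at 4 mg QOD in one paragraph and 3 in a later one. Those passages must be reconciled, but neither number enters this calculation.

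**What to change.** Add two items to SAP 9.2.4 and Appendix A.

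1. A prespecified grouped platelet term (*thrombocytopenia* or *platelet count decreased*), with each subject counted once at worst grade, by dose level. Report it for all TEAEs and for the related, serious, interruption, reduction and discontinuation summaries.
2. A summary of time to onset and episode duration for Grade 3 or higher grouped thrombocytopenia. Consecutive records of the same episode are joined across grade changes. Under Protocol 8.1.2 one record stops on the day the next starts, so the joining rule can use those dates. State whether the duration reported is the whole episode or the time at Grade 3 or higher, and give the number of episodes unresolved at final follow-up.

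The cost is one term list and two tables on data already collected, and a less favourable headline frequency. SAP Appendix A treats its table list as guidelines, so the grouped row could perhaps be added without an amendment. The episode rule should be written into the SAP before the data are summarized.

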### **9.3. Clinical Laboratory Tests**

#### **9.3.1. Laboratory Value Definitions**

Laboratory values and change from baseline values will be summarized descriptively by visit. Baseline will be determined according to Section 4.1.3. If there are multiple values that meet the criteria for baseline, additional rules may be provided after consultation with the medical monitor to delineate which value will be defined as baseline.

Laboratory test values will be assessed for severity based on the numerical component of CTCAE v4.03.

### 9.3.2. Laboratory Value Summaries

All laboratory test results and associated normal ranges from local laboratories will be converted to SI units. When there are multiple laboratory nonmissing values for a subject's particular test at a scheduled visit, the laboratory value with the smallest laboratory sequence number will be used in by-visit summaries.

Numeric laboratory values will be summarized descriptively in SI units, and non-numeric test values will be tabulated when necessary. In addition, line graphs will be provided for hemoglobin, platelet counts, leukocytes, neutrophils, lymphocytes, and blast (for hematologic tumor types as applicable).

Shift tables will be presented showing change in CTCAE grade from baseline to worst grade postbaseline. Separate summaries for abnormally high and abnormally low laboratory values will be provided when the laboratory parameter has both high and low grading criteria. The denominator for the percentage calculation will be the number of subjects in the baseline category.

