#### **Study Schedule/Procedures:**

Subjects will have regularly scheduled study visits at the clinical site as part of a 28-day cycle. Study visits are as follows:

- Screening: Day -28 through Day -1
- Cycle 1: Day 1, 4, 8, 11, 15, 22
- Subsequent cycles: Day 1 ( $\pm$  2 days; note that Day 1 must be a day with INCB059872 treatment) and Day 15 ( $\pm$  2 days)
- End of treatment: Subjects must be seen and have blood drawn 2 times per week for 2 weeks after last dose.
- Safety follow-up: 30 days (+ 5 days) after the EOT visit or last dose of study drug if EOT visit not performed (or until toxicities resolve, return to baseline, are deemed irreversible, or the subject receives another anticancer therapy, whichever is shorter).

- Follow-up for disease status (only for subjects who discontinue for reasons other than disease progression).

Laboratory tests for safety

Study visits will include sample collection for hematology, chemistry, coagulation, lipid panel, and urinalysis. Additionally, the screening visit will include serology and fertility/pregnancy testing.

Laboratory tests for PK

Pharmacokinetic [REDACTED] samples will be collected at planned visits and shipped to the sponsor or designee for analysis.

Clinical assessments

Adverse event assessments, vital signs, ECG, physical examination, ECOG performance status, and disease response assessments will be performed by the investigative site.

An objective assessment of disease status will be performed as screening, appropriate to the malignancy type (eg, CT or MRI, bone marrow biopsy/aspirate, peripheral blood, as applicable by tumor type).

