## 1.6. Potential Risks and Benefits of the Treatment Regimen

### 1.6.1. Potential Risks of INCB059872 Based on Preclinical Safety

The nonclinical safety program to support this IND was designed in accordance with ICH S9 for advanced cancer. In pivotal 1-month studies, INCB059872 was administered on a QOD regimen. The doses and dosing regimen for the pivotal GLP studies were selected based on the results of previous range-finding studies, where findings in the bone marrow (most prominent: abnormal megakaryocytes, decreased megakaryocytes) leading to marked thrombocytopenia resulted in subsequent internal and external hemorrhages in rats given  $\geq$  3 mg/kg (human equivalent dose 28.8 mg) QD and in dogs given  $\geq$  1 mg/kg (human equivalent dose 32.4 mg) QD. These observations suggested that QOD dosing may provide the best option for maximizing efficacy (which was similar after QD and QOD dosing regimens in nonclinical pharmacology studies) while minimizing toxicity (thrombocytopenia).

The primary INCB059872 toxicity findings included abnormal megakaryocyte morphology in bone marrow, thrombocytopenia, lower red blood parameters and higher reticulocytes, decreased mature granulocytes in the bone marrow and neutropenia, and increased monocyte count, and were attributed to the pharmacological activity of INCB059872. These findings were all partially or fully reversible after a 4-week recovery period. The toxicities produced by INCB059872 are similar to those described for a conditional LSD1 knockdown model in mice as described in literature ([Sprüssel et al 2012](#)), where LSD1 deficiency suppressed terminal granulopoiesis, erythropoiesis, and platelet production, with the exception of monopoiesis, which was promoted. [Sprüssel et al \(2012\)](#) also showed that peripheral blood granulocytopenia, monocytosis, anemia, and thrombocytopenia were reversible after restoration of LSD1 activity.

During the recovery period, a dose-dependent increase of platelet counts was observed. The maximum increase was about 3-fold compared to baseline values, and the peak time was approximately 14 days. The platelet counts returned to baseline values approximately 28 days after INCB059872 treatment cessation.

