**Table 8: Schedule of Laboratory Assessments**

Local Laboratory Tests	Protocol Section	Screening	Treatment						EOT	Safety Follow-Up	Notes			
			Cycle 1			Cycles 2+								
			Day 1	Day 8 (± 2 Days)	Day 15 (± 2 Days)	Day 22 (± 2 Days)	Day 1 (± 2 Day)	Day 15 (± 2 Days)						
Serum chemistries	Table 9	X	X*	X	X	X	X	X	X	X	* May be performed 3 days before the first dose.			
Hematology*	Table 9	X	X**	X	X	X	X	X	X***	X	* Must be drawn twice a week for the first 2 weeks of study treatment. In addition to Cycle 1 Day 1 and Cycle 1 Day 8, hematology samples should be drawn at Cycle 1 Day 4 ± 1 day and Cycle 1 Day 11 ± 1 day. ** May be performed 3 days before the first dose. *** Must be drawn twice a week for 2 weeks after last dose.			
Lipid panel	Table 9	X	X	X	X	X	X	X	X	X				
Coagulation panel	Table 9	X					X*		X		* Cycle 2 Day 1 and then every 3 cycles thereafter.			
Hepatitis screening	Table 9	X												
Urinalysis	Table 9	X					X*				* Cycle 2 Day 1 and then every 3 cycles thereafter			
Pregnancy test	Table 9	X*	X**						X**		All female subjects of childbearing potential. * Serum ** Urine			
PK plasma (predose)	7.8.1		X	X	X	X	X*				Collect before morning dose of study drug. * Cycle 2 Day 1, only for food-effect testing in Part 2.			
PK plasma TIMED (postdose)	7.8.1.1		X*		X*		X**				* Collect at 0.5, 1, 2, 4, and 6 hours after INCB059872 dose. Excess sample will be used for [redacted] analysis. ** Cycle 2 Day 1 only for food-effect study.			

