## **6.4. Follow-Up**

### **6.4.1. Safety Follow-Up**

The safety follow-up period is the interval between the EOT visit and the scheduled follow-up visit, which should occur 30 to 35 days after the EOT visit (or after the last dose of study drug if the EOT visit was not performed). Note that subjects will be required to submit to twice weekly blood draws in the 2 weeks after the last dose of study drug.

Adverse events and SAEs must be reported up until at least 30 days after the last dose of study drug, the date of the follow-up visit, or until toxicities resolve, return to baseline, are deemed irreversible, or the subject initiates a new anticancer treatment, whichever occurs first.

Reasonable efforts should be made to have the subject return for the follow-up visit and report any AEs that may occur during this period.

If a subject is scheduled to begin a new anticancer therapy before the end of the 30-day safety follow-up period, the safety follow-up visit should be performed before new anticancer therapy is started.

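### Unless each draw has its own eCRF visit, the SAP's by-visit platelet table and plot could miss most of a post-treatment rebound, and no visible table reports the peak count

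*SAP*

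**What the plan says.** **The effect.** Protocol 9.4.3.5, within the safety analyses, raises the chance of a rebound "effect on platelets (potentially thrombocytosis) once the drug is discontinued". The animal background is in Protocol 1.6.1, which calls the rise dose-dependent: "The maximum increase was about 3-fold compared to baseline values, and the peak time was approximately 14 days". It adds: "The platelet counts returned to baseline values approximately 28 days after INCB059872 treatment cessation".

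**The data collected.** The hematology row of Protocol Table 8 carries a footnote in the EOT cell: "Must be drawn twice a week for 2 weeks after last dose". The synopsis lists the same requirement under end of treatment: "Subjects must be seen and have blood drawn 2 times per week for 2 weeks after last dose". Protocol 6.4.1 describes the same draws within the safety follow-up period. None of the three gives the draws their own visit names or days. The extra Cycle 1 draws on Days 4 and 11, by contrast, are named in Table 8. One later count is due at the safety follow-up visit, "which should occur 30 to 35 days after the EOT visit".

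**The selection rule.** SAP 9.3.1 summarises laboratory values by visit. Under SAP 9.3.2, if a test has several values at a scheduled visit, "the laboratory value with the smallest laboratory sequence number will be used in by-visit summaries". A separate summary of high values is given only "when the laboratory parameter has both high and low grading criteria".

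**Planned outputs.** SAP Appendix A lists Table 3.3.1 (hematology summary), Table 3.3.2 (shift to worst CTCAE grade), Figure 4.6.2 (mean platelets over time), and Listings 2.8.1 and 2.8.5 (all and abnormal hematology values).

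**The concern.** The twice-weekly draws cover the period in which the animal platelet rise developed and peaked. A rule that keeps one value per visit does little harm when repeats are same-day duplicates. It matters when the repeats trace a time course of which only one point, possibly the earliest, is kept.

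Safety and tolerability is the primary endpoint of all four parts. If the later draws drop out, the platelet table and plot could look flat after treatment, and a reader could take that as evidence against a rebound although the informative counts had been taken. If humans show no rebound, what is lost is the ability to show that.

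**Working it through.** The plan states no figure to reproduce here. The check is a count of values kept, an illustration of timing, and a search for other outputs that would show the peak.

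**1. Values collected and kept.** Draws: 2 per week × 2 weeks = 4. The documents do not say how these map to eCRF visits, so there are three cases:

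| How the draws are recorded | Kept in by-visit summaries |
|---|---|
| All under one scheduled visit (EOT) | 1 of 4, by the SAP 9.3.2 rule |
| As unscheduled samples | 0 or 1 of 4: the SAP defines no visit windows and deals with unscheduled values only for baseline (SAP 4.1.3) |
| As four separate visits | 4 of 4, no loss |

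The follow-up count is kept as well, so the first case keeps 2 of 5 post-treatment counts.

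**2. What a retained early draw would show.** Inputs from Protocol 1.6.1: peak about 3 times baseline, peak at about day 14, return at about day 28. My assumptions: platelets at baseline level on day 0, the shape of the curve, a first draw on days 0 to 4 and a fourth draw on days 11 to 14.

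Share of the peak rise seen on day d:

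- Linear, d/14: day 0 = 0%; day 4 = 4/14 = 28.6%; day 11 = 11/14 = 78.6%; day 14 = 100%.
- Log-linear, (3^(d/14) − 1)/2: day 4 = 18.4%; day 11 = 68.5%; day 14 = 100%.
- Fast early, √(d/14): day 4 = 53.5%; day 11 = 88.6%; day 14 = 100%.

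As a multiple of baseline (linear, 1 + 2d/14), the first draw reads 1.00 to 1.57 and the fourth 2.57 to 3.00. If counts stand at half of baseline at the last dose (0.5 + 2.5d/14), the values are 0.50 to 1.21 and 2.46 to 3.00.

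**3. The next scheduled count.** Follow-up is 30 to 35 days after EOT, or after the last dose if there was no EOT visit. That is later than day 28, so on the animal timing it shows none of the rise.

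**4. Other outputs.**

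- Table 3.3.2 runs to the worst CTCAE grade. A high-side summary needs high grading criteria, and the documents show none for platelets.
- Protocol 9.4.3.2 plans low/normal/high shift tables only for parameters without CTCAE grades. Platelets are graded.
- Under Protocol 8.1.1, a raised count is an adverse event only if it causes signs or symptoms, is judged clinically meaningful, needs therapy or changes study drug. The last trigger falls away once the drug is stopped.
- Listings 2.8.1 and 2.8.5 are not cut to one value per visit.

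No visible planned table gives the highest post-treatment platelet count.

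**The case against.** The strongest reply is that the loss depends on material outside the two documents.

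- **Visit mapping.** The rule acts only on several values at one scheduled visit. The CRFs and sample displays are not supplied, and Protocol 6.4.1 places the draws after EOT. With separate eCRF visits nothing is lost. This stands, and makes the by-visit point conditional.
- **Which draw is kept.** That the smallest sequence number marks the earliest draw is an assumption. This stands, but an arbitrary draw would be no better for an effect that changes with time.
- **EOT timing.** Dosing may be held for up to 14 days (Protocol 5.4.7) before permanent discontinuation, so an EOT count could fall near the peak. The 0 to 29% is therefore not a full range. This stands, but an EOT column would then mix subjects at different times since the last dose, which favours windows counted from that dose.
- **Size.** The 3-fold figure is the maximum of a dose-dependent animal effect. The highest rat dose in the 1-month study was equivalent to 20.2 mg in humans, whereas Part 2 uses 3 mg every other day or 4 mg daily. This stands: the fold values are not predictions.
- **Other reporting.** Protocol 9.4.3.2 says that the incidence of abnormal laboratory values will be tabulated, and adverse events are summarised to 30 days after the last dose, which spans the animal rebound. This stands in part. SAP Appendix A lists no such incidence table, and an incidence alone does not show peak height or timing.
- **Consequence.** The analyses are descriptive, and no stated decision rule uses the by-visit platelet table. This stands and limits the weight of the point.

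A reader might also infer that the SAP has silently dropped a protocol analysis that SAP 11.1 should record. The documents do not support that: Protocol 9.4.3.5 specifies no separate laboratory analysis, only monitoring and adverse event reporting as appropriate.

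**Conclusion.** The point holds conditionally, as a cheap improvement. If the draws share one scheduled visit, or are entered as unscheduled, at most 1 of the 4 reaches Table 3.3.1 and a visit-based Figure 4.6.2. With animal-like timing and an early retained draw, those outputs would show 0 to 29% of the peak rise on a linear curve (0 to 18% log-linear, 0 to 53% fast early). Human size and timing are not in the documents.

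It would go too far to say that the rule certainly discards three of four counts, or that a rebound would go unrecorded. The first needs the eCRF visit structure. The second is contradicted by the listings and by the adverse event route for clinically meaningful rises. That Figure 4.6.2 is plotted by visit is also an inference from its title and SAP 9.3.1.

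One part needs no assumption about mapping: no visible planned table summarises the highest platelet count after the last dose. Platelet falls are not at issue.

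**What to change.** In SAP 9.3.2:

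1. Exempt hematology after the last dose from the smallest-sequence rule.
2. Assign every such value, scheduled or unscheduled, to windows counted from the last dose (for example days 1–4, 5–8, 9–11, 12–16, and follow-up), and use these in the by-visit table and the platelet plot.
3. Add one table, by group and dose, of the maximum platelet count after the last dose: ratio to baseline, and n (%) above the upper limit of normal. Use only values before any new anticancer therapy.

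The change belongs in the body of the SAP. Appendix A lets the list of outputs change, but the selection rule sits in 9.3.2.

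The cost is some wording, one window definition and one table, from counts that the protocol already requires. There are no new draws, subjects or visits. Windows will be sparse in small dose cohorts and where subjects do not return or start new therapy. In AML and MDS, disease and transfusion also move the counts, so the solid-tumor groups, with an entry floor of 100 × 10⁹/L, will be the easiest to interpret.
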